### **9.6.2 Key Secondary Hypotheses**

For the key secondary hypotheses, a high level statistical analysis plan is described below. Further details and specifications regarding the assessment of each hypothesis will be provided in a formal statistical analysis plan prior to data lock.

**Functional Key Secondary Hypotheses:** *Children treated with AFQ056 will show greater normalization of specific measures of language and one or more other domains (including cognitive, adaptive behavior, global functioning based on change from baseline (visit 3 assessment) to 8 months (visit 9 assessment) than those treated with placebo.*

All of the key secondary functional outcomes are measured on scales similar to that of the weighted communication score primary outcome. All key secondary functional hypotheses generally state that there will be greater improvement in language, communication, cognitive, developmental, and adaptive functioning in the AFQ056-treated group over the placebo group during an 8-month period [baseline (visit 3 assessment) to 8 months (visit 9 assessment)]. Each scale produces a numeric score that can be assessed in a manner similar to that described for the assessment of the primary endpoint in section 9.6.1.

### **9.6.3 Exploratory Hypotheses**

**Biomarker Exploratory Hypotheses:** *Children treated with AFQ056 will show greater improvement of these specific ERP and eye tracking measures based on change from baseline (visit 3 assessment) to 8 months (visit 9 assessment) than those treated with placebo.*

For the biomarker assessments, the ERP requires data processing centrally but eventually provides a score that can be assessed in a manner similar to that described for the assessment of the primary endpoint in section 9.6.1. The eye tracker produces two important outputs relevant to these hypotheses – the percent of looking time to eyes and the number of fixations to the eyes. We expect both to be essentially continuous variables, and feel confident that they can also be assessed in a manner similar to that described in section 9.6.1.

A number of additional exploratory hypotheses can be considered using the data produced from this study. These will include, but are not limited to:

- Examine whether the same effects observed for the overall population are also observed for the group of males only enrolled into the study. With the anticipated enrollment of about 80 males and 20 females, power should be sufficient to analyze the male-only group.
- Examine whether one or more blood biomarkers will be abnormal in FXS, and will normalize in children treated with AFQ056 relative to those treated with placebo.
- Biomarker (ERP, eye tracking/pupillometry, molecular/cellular) responses, if present will be evaluated for correlation with responses on clinical measures and with drug levels from PK determinations, in order to determine whether biomarkers track with and predict clinical and/or pharmacological responses to provide clinical and pharmacological validity data for future work.
- Examine whether blood levels of AFQ056 will correlate with improvement in language, functional, and biomarker measures relative to baseline throughout the study.
- Clinical responses and side effects presumed likely due to AFQ056 will be evaluated for correlation with drug levels from PK analyses.
- Longitudinal analysis to determine whether the rate of change in language, functional, or biomarker responses in the group assigned to placebo will be lowest during the first 6 months of the study (Screening to visit 5/month 2), higher in the next 6 months with the language intervention (visit 5/month 2 to visit 9/month 8), and highest in the final 8 months with both the language intervention and AFQ056 treatment (visit 9/month 8 to visit 14/month 16) – with inflection points at visit 5/month 2 when the language intervention is started and visit 9/month 8 when AFQ056 is started.
- Analyses of change from baseline at the 2 month visit (visit 5) will be evaluated for all clinical and biomarker outcomes, to determine if effects of drug alone can be identified before the language intervention is initiated. Likewise analyses of change from baseline and from the final visit before weaning treatment with AFQ056 (16 month visit, visit 14) at the Follow Up visit (visit 15) will be evaluated for all clinical and biomarker outcomes, to determine if regressive effects of coming off drug are evident. Covariates in the analyses will be medication (coded as a factor with a small number of levels), age, and additional variables that are shown to be imbalanced through unlucky randomization.

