At the end of 4 months in the placebo lead-in all subjects will have a repeat battery of assessments and be randomized to drug or placebo at an AFQ baseline visit. The initial dose will be 25 mg BID and dose titration will be done every week based on safety report and side effects alone (efficacy will not be a factor in dose titration due to known strong early placebo effects in prior FXS studies). If the subject has no side effects at each call, the dose will be force titrated (mandatory titration if no side effects) to the next level, 50 mg BID, 75 mg BID and 100 mg BID in order. If there is concern for side effects the dose may be left the same for an additional week or reduced. If there are side effects after the first week of treatment, the 25 mg dose will be allowed to be reduced to 12.5 mg BID. Patients who cannot tolerate 12.5 mg BID will be withdrawn from the study. Subjects will be seen for a study visit for a safety check at 1 month from baseline, during the titration period. The dose can be adjusted weekly through week 7 after baseline. This will give extra weeks after the full titration schedule to ensure the final dose chosen is the optimal one for the given patient. After 7 weeks, the dose will be fixed and at the 2 month visit (language intervention baseline visit) all subjects will have the battery of assessments again and will initiate the language intervention, remaining on a stable AFQ056/placebo dose for the next 6 months.

Families will have training for the language intervention at the 2 month visit, and subsequent instruction and monitoring of delivery of the intervention will occur by weekly video conferencing (per institutional policy) with the language therapist for the first 4 months of the intervention (6 months from randomization), and then monthly for the duration of the study.

Study visits will occur at the 3, 4, 6 and 8 month visits (v6 – 9) after implementation of the language intervention (occurs at 2 months).

- At 3 months: only VAS and CGI assessments will be done
- All baseline assessments except the Mullen, PLS-5, and Children's Sleep Habits Questionnaire will be repeated at 4 and 6 months (visits 7 and 8). Auditory ERP and Eye Tracking will only be repeated at 4 months (visit 7) and not at 6 months (visit 8).
- All baseline assessments will be repeated at the 8 month visit (visit 9), in addition to the EKG and blood/urine tests.

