Once a subject is randomized and a kit assigned, the parent/caregiver will continue to receive at every 2-month in-person study visit bottles containing 500 mg of active drug or matching placebo powder, as well as bottled water and premarked 60 cc syringes with 50 cc fill line to use for reconstitution of the AFQ056 powder. Subjects will start on 25 mg BID (2.5 cc BID) or matching placebo after randomization and the dose will be titrated weekly depending on tolerability. If the subject has no side effects at each call, the dose will be force titrated to the next level, 50 mg BID, 75 mg BID and 100 mg BID in order. If there is concern for side effects the dose may be left the same for an additional week or reduced. If there are side effects after the first week of treatment, the 25 mg dose will be allowed to be reduced to 12.5 mg BID. See section 9.1 also for dose adjustment considerations. Patients who cannot tolerate 12.5 mg BID will be withdrawn from the study. Subjects will be seen for a study visit for a safety check at 1 month from baseline, during the titration period. The dose can be adjusted weekly through week 7 after baseline. After randomization, monitoring procedures to ensure correct reconstitution

with parent/caregivers will be identical to those described above for the placebo lead-in. Drug accountability/compliance will be assessed at every 2-month in-person visit after Baseline (i.e. when drug is dispensed). Parents/legal guardians should be reminded to bring all study drug bottles with them to each 2-month visit when drug accountability is to be done. For more details, please refer to the Study Medications/Central Pharmacy section of the Manual of Operations.

The following table provides recommendations and guidelines regarding dose titration. Please note the Site Investigators will have the opportunity to contact the Independent Medical Monitor (IMM) should they be unclear as to how to proceed, and need additional input and guidance. Details about how to contact the IMM can be found in the Manual of Operations.

AE Grade/Severity	Relationship	Most Likely Drug Action	Possible Other Drug Actions						
Grade 1 (Mild)									
	Unrelated	Increase							
	Unlikely	Increase							
	Possibly	Increase							
	Probably	Increase	Hold at physician discretion if AE non tolerable for patient/family and/or concern for worsening AE with increase						

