The suspension will be drawn up into a syringe fitted to the cap on the bottle in which the powder has been reconstituted and administered directly into the subject's mouth at home and in the outpatient setting by the parent/caregiver. The subject should swallow after the suspension is administered, and the subject's mouth should be checked to ensure that the suspension was swallowed. Approximately 8 oz. of fluid (e.g. water, juice, milk) will be administered with the drug administration. If the child does not tolerate having the suspension administered directly with the syringe, the suspension may be mixed with fluid (e.g. water, juice, milk) and then given to the child. The parent/caregiver will fill out a medication diary to indicate every dose administered to the child. All dose changes during the study will be recorded on a Dose Titration CRF and captured in the EDC.

Doses in the range of 1.25 ml (12.5 mg) to 10 ml (100mg) twice daily will be administered orally during the study. The dose will be given in the morning and early evening. The two doses should not be taken less than 4 hours apart. If insomnia is a side effect the second daily dose may be moved to early afternoon.

Expected side effects would be those observed in the prior adult/adolescent studies in FXS and the pediatric PK study. These include dizziness, insomnia, headache, decreased appetite, vomiting, diarrhea, and behavioral “activation” with irritability, aggression, hyperactivity, anxiety, and impulsive behavior. These side effects are expected to be relatively infrequent, mild-moderate in degree, and insomnia and behavioral side effects will in most cases be manageable by dose adjustments in the flexible dosing period. Insomnia may be managed by moving the dose earlier in the day as noted above.

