### **6.3.11 Pharmacokinetic Studies**

Pharmacokinetic assessment will be done for AFQ056 for all patients at screening, 2, 8, 10, and 16 month visits (visits 1, 5, 9, 11, and 14) by collecting blood for PK after safety labs are drawn. Blood samples will be drawn prior to dosing of the PM AFQ056 dose. The date and time of blood collection will be recorded on the PK blood collection page in the source documents and CRF, together with the date and time for the past three doses and the time of the last meal immediately preceding the PK sampling time.

If the PK blood samples cannot be collected at the screening visit, sites may collect them at the -2 month or baseline visits (v2 or v3) as long as it is prior to randomization. If the PK blood samples cannot be obtained at a visit occurring post-randomization (v5, 9, 11 and 14), then the samples may be collected at the next visit to the site.

PK Samples from all sites will be batched and shipped twice, in shipments midway through the study, and at the end of the study. The study sites will be notified by the Study Team site when to prepare and ship samples. The CCC Central Lab will provide tubes and materials for PK collection from subjects, shipping materials, labels, and a Fed Ex account number for shipping PK tubes from sites to the CCC Central lab. One batch of tubes will be shipped to the CCC Central Laboratory at University of Rochester in batches from each study site midway through the study and at the end of the study. The second batch of tubes will be held at the site until the CCC Central Laboratory notifies the site that the first batch of tubes have arrived and been inventoried and stored. After the notification, the sites will then ship the corresponding second batch of tubes to the CCC Central Laboratory.

After all samples have been collected and received from the sites, the CCC Central Laboratory will ship them internationally to Veeda lab analysis of AFQ056 levels. Veeda was identified by Novartis and has been used for PK measurements to quantify AFQ056 in plasma samples for previous Novartis studies.

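### Side effects are to be correlated with AFQ056 levels drawn after side effects have set the dose, so for dose-changing events the correlation is biased downward and a true relation can be missed

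*Combined protocol and SAP*

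**What the plan says.** Section 9.6.3 lists, among the exploratory hypotheses, that "Clinical responses and side effects presumed likely due to AFQ056 will be evaluated for correlation with drug levels from PK analyses". It gives no window for the side effects, no rule for which level to use, and no adjustment for dose or time. The covariates named at the end of that section (medication, age, chance imbalances) do not address the point.

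Section 3 says that "dose titration will be done every week based on safety report and side effects alone". A child without side effects must go up, through 50 and 75 to 100 mg BID. Otherwise: "If there is concern for side effects the dose may be left the same for an additional week or reduced". The window then closes: "The dose can be adjusted weekly through week 7 after baseline". The same titration is repeated between months 8 and 10 (section 6.3.14).

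Section 6.3.11 sets the sampling: "Pharmacokinetic assessment will be done for AFQ056 for all patients at screening, 2, 8, 10, and 16 month visits". If a post-randomization sample is missed, "then the samples may be collected at the next visit to the site", which is later, not earlier. No level is scheduled inside a titration period.

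Section 5.1 gives a titration table by grade and relatedness, and adds: "All dose changes during the study will be recorded on a Dose Titration CRF and captured in the EDC".

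**The concern.** A correlation between side effects and drug level is naturally read as evidence on whether higher exposure causes harm. Here the order is reversed for part of the data. A child whose side effect led to a hold or a reduction arrives at month 2 on a lower dose because of it; a child without side effects arrives on 100 mg BID. The level then carries information about the event that came before it, and that information runs against a true positive relation.

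Better-timed samples or a fixed visit would not cure this. Section 9.3 already says that side effects have shown little correlation with levels in earlier AFQ056 studies. A null result produced by titration would look like confirmation, in an age group for which section 2.1 says extended safety data are lacking.

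**Working it through.** The plan states no figure for this correlation, so there is none to reproduce.

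**1. Order of events.** Titration ends at week 7, or day 49. Month 2 is about day 61; with the 5-day window the earliest visit is day 61 - 5 = 56. The first on-drug level therefore follows the close of titration. Month 8 is on the same fixed dose, and a child who needs a reduction between months 2 and 8 is withdrawn (sections 6.2.3 and 7). Months 10 and 16 follow the second titration, and section 6.3.14 also allows reductions in the open-label period.

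**2. Is there a relation to miss?** Table 4 pools trials with assigned doses (placebo, 25, 50, 100 mg BID).
- Any adverse event: 53/86, 50/75, 43/69, 71/84 = 61.6%, 66.7%, 62.3%, 84.5%; Cochran-Armitage trend z = 3.2.
- Insomnia: 0/86, 1/75, 4/69, 14/84 = 0%, 1.3%, 5.8%, 16.7%; z = 4.9.

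A dose-toxicity relation is plausible.

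**3. How strongly does a side effect change the dose?** From the section 5.1 table:
- Grade 1: increase is the default at every level of relatedness. For probable or definite events the alternative reads "Hold at physician discretion if AE non tolerable for patient/family and/or concern for worsening AE with increase".
- Grade 2: increase up to possibly related; hold if probable or definite, with decrease if intolerable.
- Grade 3 or higher: decrease if probable or definite; hold if unlikely or possible.

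Section 6.3.14 lets the dose rise again once an event has resolved or clearly improved. It also says that clinically significant new problems or worsening lead to a decrease, which is stronger feedback than the table. The two must be reconciled, because they govern the size of the bias.

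**4. Size, graded simulation.** Model: logit P(side effect in week w) = a + b·log2(concentration) + child effect, with exp(b) = 2 or 3 and concentration = dose × child PK factor, followed through 7 weekly titration steps. Inputs: 50 treated children (half of 100), and PK CV 45%; Tables 2 and 3 show AUClast CVs of 24.3% to 58.2% in groups of two or more. Assumed, not in the documents: grade mixes from 80/17/3 to 40/40/20 (Grades 1/2/3), event rates and child sensitivities. The result is the correlation of any titration-period side effect with the end-of-titration level.

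| Dose rule | Mean correlation | Significantly positive |
|---|---|---|
| Randomly assigned doses | +0.26 to +0.45 | 47-92% |
| Section 5.1 table, free re-escalation | +0.10 to +0.26 | 10-44% |
| Same, Grade 2 or higher only | - | 5-28% |

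Under the table rule, significant reversal occurred in at most 1% of trials. Runs with other assumed rates gave:
- about +0.32 to +0.52 with random doses;
- +0.16 to +0.39 with table-like feedback;
- about -0.05 to +0.16 for Grade 2 or higher when reductions for severe events are kept;
- -0.23 to -0.42 when every side effect causes a reduction that is kept.

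**5. Cross-check, threshold model.** A side effect occurs when the level exceeds the child's own threshold (PK CV 40-50%, no background events). A positive relation is built in throughout.

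| Children reduced and capped after a side effect | Mean correlation |
|---|---|
| Random doses (comparator) | +0.27 to +0.55 |
| None | +0.20 to +0.47 |
| Half | -0.16 to +0.18 |
| All | -0.04 to -0.56 |

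The row with no reductions stays close to the comparator, so most of the loss comes from the feedback.

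**6. Does time-matching help?** Using the concentration predicted for each week (dose in force × month 2 level per mg) on all weekly records, with 40-50 children and half or all of them reduced after a side effect, the slope had the true sign in 84-100% of threshold-model trials. It was never significantly reversed, and power was 29-100%. In the same trials the bare correlation averaged -0.49 to +0.07 and was significantly positive in at most 8%. A first-onset version stratified by week gave an odds ratio per doubling of about 1.0 when the truth was 1, 1.2-1.5 when it was 2, and 1.4-1.8 when it was 3. On the log scale that recovers ln 1.2/ln 2 = 26% to ln 1.5/ln 2 = 58% of the effect.

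**The case against.** The strongest reply is that the table makes increase the default for mild events, and events in the earlier studies were mostly mild: all were mild in the pediatric PK study and mild to moderate in adults and adolescents (section 2.2). With little feedback the correlation stays positive. This stands, and it limits the point to dose-changing events.

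A reader might infer that the correlation will come out reversed. The documents do not support that. Reversal needs reductions that are common and kept, whereas the table reserves decrease as the default for Grade 3 or higher probable or definite events, and section 6.3.14 allows re-escalation. Even with kept reductions, widening the PK CV to 65% shrinks the result to -0.20 to -0.38 at a true odds ratio of 2.

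A reader might also infer that the trial's safety conclusions are compromised. They are not: section 9.7 compares adverse event frequencies by randomized arm over the 8-month blinded period.

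Two further replies stand in part. Section 9 defers detail to a formal SAP, and section 9.6.3 fixes no window or model; but nothing in the text addresses the issue, and the bare wording invites the simple correlation. Children still on drug at a termination visit have the month 16 procedures, which include PK, so some withdrawn children do have a level. Those who stopped drug first have only safety assessments listed, without PK.

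**Conclusion.** The concern holds in limited form. For side effects that hold or lower the dose, the planned correlation is biased downward. Under feedback like the section 5.1 table, a true relation is attenuated and often missed: 10-44% of simulated trials detected it, against 47-92% with random doses. For Grade 1 events the bias is weak.

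The direction follows from the documents. The size rests on assumed grade mixes, event rates, sensitivities and PK variability, and on how sections 5.1 and 6.3.14 are reconciled. The primary test, the sample size and the randomized safety comparison are untouched. What is at risk is a mistaken exploratory conclusion that side effects are unrelated to exposure.

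**What to change.** Keep side effects in the section 9.6.3 bullet and replace the bare correlation with a time-matched analysis:

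- In AFQ056-exposed records, model first onset of drug-attributed side effects by titration week: logit P(first onset in week w) = α_w + β·log2(predicted concentration). Predicted concentration is the dose in force that week, from the Dose Titration CRF, times the child's measured level per mg.
- Report by adverse event grade.
- Tabulate first-onset rates by nominal dose step in both arms, including children with no level. Placebo children follow the same nominal steps and so control for time.
- State that an unadjusted correlation with post-titration levels cannot be read as absence of a concentration-toxicity relation.
- Reconcile the section 5.1 table with the dose-decrease sentence in section 6.3.14.

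The cost is SAP wording and modest modelling on data already captured, with no change to dosing or sampling. The limits should be stated. Noise in level per mg attenuates the estimate. The method assumes roughly dose-proportional exposure within a child, which section 2.2 states from adult data but the documents do not show in these children. Children with no on-drug level enter only the table.

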**Number of Arms:** The number of arms to be employed in this trial was carefully considered, including possible 2-, 3- and 4-arm designs. The 3-arm design would include an AFQ056 group with language intervention, a placebo group with language intervention and a placebo group with treatment-as-usual. Although this would have resulted in information about the effectiveness of the language intervention alone, families would know if they are getting a language intervention, and it would have been very hard to keep such a trial blinded. A 4-arm design was considered modeled after Compton et al. in a study of SSRI treatment and behavioral therapy for OCD, with treatment-as-usual and language intervention groups for both placebo and AFQ056 groups, however in the Compton study the pharmacotherapy and behavioral therapy were considered potentially equivalent interventions from an efficacy standpoint, **while in this trial the main hypothesis is that the AFQ056 will enhance learning in young children with FXS and the language intervention is being employed to push learning rate and “plasticity” and provide a substrate for the drug to act upon.** Thus, this trial is conceptually different from that in the Compton study and the 4-arm design is not critical to the hypothesis. Given the hypothesis and the need to increase the trial size to at least 160 participants for a 4-arm trial, the 2-arm trial with the language intervention with placebo and AFQ056 groups was chosen to maximize power to evaluate the key conditions, minimize cost and to maximize feasibility in a rare disease. However, given the value of understanding the effects of the language intervention itself, a placebo lead-in incorporated into the trial will allow comparison of 6 months of placebo treatment with and without the language intervention in the group randomized to placebo (see paragraph below). Further, all outcomes including the primary outcome will be evaluated at visit 5, two months after baseline when subjects are at MTD, before starting the language intervention, to determine if the AFQ056 has had an early independent effect on outcomes in the absence of language learning intervention.

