## 9.4 Randomization

In order to prevent age imbalance, randomization will be stratified by age with two strata, 3-4 years and 5-6 years. Block randomization will be used with random block sizes, and age (coded as a two-level factor) will be used as a covariate in all statistical analysis. The stratification will ensure that all individuals enrolled will have a Mullen ELC (equivalent to Developmental Quotient) of <75. This will ensure sufficient symptoms to measure learning improvement and will result in enrollment of only significantly affected females, most likely excluding at least the higher functioning half of females with a full mutation (because of this, females are expected to comprise about 20% of study participants). Likewise, very high functioning males (the best functioning 10-20%) will be excluded. Thus, the males and females enrolled are expected to show heavily overlapping clinical phenotypes and developmental function and stratification is expected to be unnecessary. Further, there is no reason to expect a priori a difference in response in lower versus higher functioning individuals within the impaired group with delays enrolled, and thus even if the females are on average higher functioning within the impaired range than males, it is not clear they will respond sufficiently differently to justify stratification in a randomized design.

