## 9.6 Statistical Analysis Plan

### 9.6.1 Primary Hypothesis

**Primary Efficacy Hypothesis:** *Children treated with AFQ056 will show greater improvement in language and its nonverbal communicative precursors as reflected in on change in a weighted communication score designed to assess both the proclivity to engage in communication and the sophistication of the means employed for communication from baseline (visit 3 assessment) to 8 months (visit 9 assessment) than those treated with placebo.*

The study design is longitudinal involving unequally spaced data collections over the placebo-controlled phase at 0 (baseline), 2, 4, and 8 months (see Figure 2). Focus is on the difference in the rate of change among the placebo (PL) and treatment (TX) groups. To account for the model design and potential dropout, linear mixed models (LMMs) will be used for the analysis.

Suppose that  $Y_{ij}$  is the outcome (e.g., language score) for the  $i^{\text{th}}$  participant ( $i = 1, \dots, N$ ) at the  $j^{\text{th}}$  time point ( $j = 1, \dots, T_i$ ). Assuming linear change over time, the LMM can be written as:

$$Y_{ij} = \beta_0 + \beta_1 t_{ij} + \gamma_0 g_i + \gamma_1 t_{ij} g_i + (b_{0i} + b_{1i} t_{ij} + e_{ij}) \quad (1),$$

where  $g_i = 1$  if the participant is in TX and 0 if in PL,  $t_{ij}$  is time in months,  $b_{0i}$  and  $b_{1i}$  are random effects,  $e_{ij}$  is random error, and the remaining parameters are fixed effects. We make the typical normality and related assumptions for the random effects and random error. Due to randomization, there is no average intercept difference and we set  $\gamma_0 = 0$ . The mean longitudinal change is then: for PL is then:

$$\text{For PL: } E(Y_{ij})_{\text{PL}} = \beta_0 + \beta_1 t_{ij} \quad (1a),$$

$$\text{For TX, } E(Y_{ij})_{\text{TX}} = \beta_0 + (\beta_1 + \gamma_1) t_{ij} \quad (1b).$$

The target of inference is  $\gamma_1$  that represents the mean difference in rate of change among the groups. For the primary language endpoint, treatment efficacy occurs when  $\gamma_1 > 0$ , because language is acquired at a faster rate for TX (cf. Equations 1a and 1b). Therefore, the primary null hypothesis for the analysis is:

$$H_0: \gamma_1 = 0.$$

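### The month-2 analysis of drug effect before the language intervention does not pre-specify adjustment for the visit-3 value of the outcome: a free gain in precision, of uncertain size

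*Combined protocol and SAP*

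**What the plan says.** Section 9.6.3 lists the month-2 comparison among its exploratory items: "Analyses of change from baseline at the 2 month visit (visit 5) will be evaluated for all clinical and biomarker outcomes". Section 9.3 (Number of Arms) gives its purpose: "to determine if the AFQ056 has had an early independent effect on outcomes in the absence of language learning intervention".

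The same item in 9.6.3 sets out the adjustment: "Covariates in the analyses will be medication (coded as a factor with a small number of levels), age, and additional variables". The list is then left open to "additional variables that are shown to be imbalanced through unlucky randomization". It does not say whether medication means the randomised arm or concomitant drugs. Section 9.4 adds one general rule: "age (coded as a two-level factor) will be used as a covariate in all statistical analysis". Neither place names the outcome's own value at visit 3, and 9.6.3 writes down no model for month 2.

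Table 7 (Section 6.1) schedules the weighted communication score, ERP, Mullen, Vineland, PLS-5, MacArthur, VAS, ABC-FX and eye tracking at both visit 3 and visit 5, so the covariate will exist for most outcomes. The primary model in 9.6.1 treats baseline differently: visit 3 is one of the responses and the arms share an intercept ("Due to randomization, there is no average intercept difference").

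**The concern.** Subtracting baseline fixes its coefficient at 1. When spread is similar at the two visits and they correlate below 1, the best coefficient is ρ, which is smaller. The change score then over-corrects. It carries extra noise, and in any one trial its estimate moves with chance baseline imbalance.

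Visit 5 is the only planned full-battery randomised comparison before the language intervention, so it carries the attempt to see a drug effect by itself. Section 6.3.15 expects about half the children to complete ERP and eye tracking, roughly 25 per arm (0.5 × 50), and precision is scarcest there.

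The clause admitting imbalanced variables does not settle the matter. Adjustment gains precision because baseline predicts the outcome, whether or not the arms look imbalanced. A trigger with no stated threshold also leaves the choice until after the data are seen.

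**Working it through.** **The plan's own figure.** None is stated for month 2. The 50 per arm in Section 9.8 is for the primary slope difference. It cannot be rebuilt because the placebo slope and variance components are not reported. Nothing below contradicts it.

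**Inputs.**
- 50 per arm, 80% power and alpha 0.10: Section 9.8, set for the primary endpoint and borrowed here as a yardstick. The one-degree-of-freedom chi-squared test makes alpha two-sided.
- Correlation ρ between visits 3 and 5: not given. The nearest figure is the Mullen test-retest range 0.76–0.96 (Section 6.3.9), which is not a two-month correlation in this population. Assumed range: 0.3–0.96.
- SDs: assumed equal at first, then varied.

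**Step 1: variances.** With unit SD at both visits, the per-child variance is 2(1−ρ) for a change score and 1−ρ² = (1−ρ)(1+ρ) after baseline adjustment. The ratio of adjusted to change-score variance is (1+ρ)/2.

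**Step 2: power.** Choose the effect that gives 80% power under adjustment. Its standardised size is 1.645 + 0.842 = 2.487. Under the change score this becomes 2.487 × √((1+ρ)/2), and power is Φ(that value − 1.645). At ρ = 0.5: 2.487 × 0.866 = 2.153, and Φ(0.509) = 69.4%. The number per arm that restores 80% is 50 divided by the variance ratio, e.g. 50/0.75 = 66.7, rounded up to 67.

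| ρ (assumed) | Variance ratio | Change-score power | N per arm for 80% |
|---|---|---|---|
| 0.3 | 0.65 | 64.1% | 77 |
| 0.5 | 0.75 | 69.4% | 67 |
| 0.7 | 0.85 | 74.1% | 59 |
| 0.76 | 0.88 | 75.4% | 57 |
| 0.9 | 0.95 | 78.2% | 53 |
| 0.96 | 0.98 | 79.3% | 52 |

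At alpha 0.16, the other level in Section 9.8, the powers at ρ = 0.5 and 0.7 are 70.6% and 74.7%.

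**Step 3: unequal spread.** With SDs s1 and s2 the ratio is s2²(1−ρ²) / (s1² + s2² − 2ρ·s1·s2). Section 6.3.9 quotes communication-score SDs of 6.29 and 20.50, nine months apart, in children with autism. These give 1.00 (no loss) at ρ = 0.3 and 0.35 at ρ = 0.9. The loss can therefore vanish or be much larger than in the table.

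**Step 4: chance imbalance.** At 25 per arm, one standard error of the baseline difference is √(2/25) = 0.28 SD. At ρ = 0.5 an imbalance of that size puts the change-score estimate (1−0.5) × 0.28 = 0.14 SD away from the adjusted one, in either direction.

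**Step 5: the mixed-model alternative.** Take two visits, a common baseline mean, a free visit-5 effect, ρ = 0.5 and 50 per arm. The variance of the visit-5 contrast is 0.030. Baseline adjustment gives 2(1−0.25)/50 = 0.030; the change score gives 4(1−0.5)/50 = 0.040. This model loses nothing.

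**Step 6: does Equation 1 already supply it?** Not as written. One slope difference γ1 runs over months 0 to 8, so the arm contrast is 2γ1 at month 2 and 8γ1 at month 8. The month-2 contrast is a quarter of the month-8 contrast by construction and is not estimated separately.

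**The case against.** The strongest reply is that 9.6.3 names no model. Section 9.6.1 also speaks of change from baseline to month 8 and then uses a mixed model with baseline among the responses. Sections 9.6.2 and 9.6.3 extend that approach to the 8-month secondary and biomarker hypotheses. In such a model baseline would never appear in a covariate list, so its absence does not prove it is unused. This stands in part, and it makes the loss conditional. However, the extension is not made expressly for month 2, and Equation 1 over 0–8 months does not isolate that visit. Fitted to visits 3 and 5 alone, its fixed part would become the no-loss model, but the plan does not say this is done.

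It can also be said that the item is exploratory ("A number of additional exploratory hypotheses can be considered using the data produced from this study"), that no power is claimed for it, and that Section 9 promises a formal analysis plan. All true: no stated figure becomes wrong, and this is an improvement rather than an error.

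Four stronger readings might be inferred, and the documents do not support them:
- That power is definitely lost. This depends on an unstated model and an unknown ρ.
- That the result is biased. Under randomisation the change score is unbiased; only efficiency is at issue.
- That visit 5 is the only randomised look without the language intervention. VAS, CGI and the sleep questionnaire are also taken at month 1.
- That the visit-3 value can be added for every outcome. Section 6.3.9 has CGI-I rated relative to visit 3 once that visit has passed, so it has no visit-3 level of its own. Blood biomarkers are scheduled at screening, not visit 3 (Table 7, footnote 2; Section 6.3.12).

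**Conclusion.** The point holds in conditional form. As written, 9.6.3 does not pre-specify baseline adjustment for the visit-5 comparison. A change-score analysis with the named covariates would be valid but, in large samples, never more precise than an adjusted one.

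With equal spread, 50 per arm and alpha 0.10, the cost against an adjusted analysis with 80% power is about 11 points at ρ = 0.5, 6 points at ρ = 0.7, and 1 to 5 points over the Mullen test-retest range. These figures rest on an assumed ρ, assumed equal SDs, and design values borrowed from the primary endpoint. With changing spread the cost can be nil or larger. It is nil under a mixed model with a common baseline mean and a free visit-5 effect. The primary analysis is unaffected.

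**What to change.** In Section 9.6.3, or in the formal analysis plan, name the visit-5 model. Either of these will do:
- regress the visit-5 value (or the change) on arm, age stratum and the visit-3 value of the same outcome, pre-specified whether or not the arms look imbalanced; or
- take the visit-5 contrast from a repeated-measures model with a common baseline mean and a free visit-5 effect.

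For blood biomarkers use the pre-randomisation (screening) value. State that CGI-I is exempt because it is itself a rating of change. Describe visit 5 as the only planned full-battery randomised comparison before the language intervention.

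This is a free improvement: one sentence and one degree of freedom, with no new data. At 25 per arm that is one of about 47 residual degrees of freedom (50 children less intercept, arm and age stratum), or about 2%. That would offset the gain only at ρ near 0.96, where the variance saving is itself 2%.
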